To promote retention, participants will be contacted at two and five months by Project HEAL staff members, who will remind the participant of the study timeline, indicate when the next assessment will be completed, and remind the participant that he/she will be assigned to an active intervention after the 6-month study period.

Addressing mentee/mentor mismatch: There is a 3-step procedure for addressing instances in which a mentee reports a mismatch with his/her mentor. First, the mentor would receive supervision and make attempts to resolve the mismatch. Second, if the mismatch persists, we will match the mentee with a new mentor one time only. If a mentee has a mismatch with their second mentor, they will not be eligible to be re matched and their participation in the study interventions (mentorship) will be discontinued. If the mismatch occurs because the mentee is not abiding by guidelines for participation and this causes the mentor to feel uncomfortable, the PI/Co-I will speak with the mentee to address the issue. If this persists, the mentee's participation in the mentorship component of the study will be discontinued. Mentee guidelines are attached.

Operationalized criteria for early discontinuation of the active intervention: Grounds for discontinuing the active interventions (meaning that the participant is no longer able to meet with his/her mentor) include the following:

- (a) Not complying or attending outpatient treatment (defined as mentee or provider indicating that the mentee is not attending treatment for 2 weeks or more) *or* not hearing from the mentee's treatment provider for 2 consecutive months.
- (b) Requiring a higher level of care (per the mentee's treatment provider) and choosing not to pursue it.
- (c) Missing 3 consecutive sessions with mentor and/or missing >2sessions/month for 2 consecutive months (without calling ahead to reschedule).
- (d) Requesting >1 mentor reassignment. If the mentee has a mismatch with >1 mentor, we will not be able to assign a third mentor.

If a mentee is recommended for, and enters, treatment at a higher level of care, he/she may not receive mentorship while receiving treatment at the higher level of care. After discharge, pt may attend any remaining mentorship sessions falling within the study period (months 1 – 6) after providing a new provider clearance form. If the mentee was assigned to the wait list and enters treatment at a higher level of care during months 6 – 12, the same procedure will be followed. We will ask study participants to continue completing questionnaires even if a participant is no longer meeting with his/her mentor (regardless of the reason). Patients may choose whether they wish to continue completing study assessments.

Common intervention components

Recovery Record: Participants in the peer mentorship arm of the study will be asked to utilize Recovery Record®, a HIPPA-compliant smart phone and/or computer application, as a recovery tool only. No data will be collected using this application. The application was designed to provide support to eating disorder patients and includes a number of features aimed to promote recovery, such as a meal tracking record, prompts for completing meals/snacks, tracking for additional symptoms such as stress and mood, motivational messages, information about coping strategies, and capacity to share logged data with clinicians and mentors. Participants in the social support and wait-list control interventions will be informed that Recovery Record® has a number of additional features that they are welcome to explore on their own or in collaboration with their outpatient treatment team. Using the app will not be required if a participant prefers not to use it.

Community support groups: All participants in the study are invited to attend Communities of HEALing support groups, which are offered by Project HEAL but they are not part of the proposed study. Groups may include members of the community who are not involved in research. Participants will be informed at the onset of groups that there are members in the group who are not participating in the research study and it will be up to their discretion whether they choose to attend.

Mentor Training:

Peer mentors: Peer mentors receive 23 hours of training in an online “classroom” which includes completing readings, watching lectures, videos, film clips and role plays, as well as completing writing assignments. Training topics include: general information/history regarding peer mentorship interventions generally and Communities of HEALing specifically,

overview and in depth review of the [name] peer mentoring manual (8 keys), crisis responding, and training in human subjects research, including the specifics of the current study.

Social support mentors: Social support mentors receive training in the rational and procedures of the social support intervention, crisis responding, and general and study-specific research training components. Social support mentors do not receive training in core peer mentorship components. Social support mentor training is 4-5 hours.

In both groups, 2.5 hours of the mentor training is devoted to recognizing and responding to urgent/emergency situations. Training is coordinated by Project HEAL staff. The PI and Co-I will develop and lead training regarding research components.

Fidelity monitoring and supervision: Drs. [name] or [name] will provide supervision for mentors in both active conditions (peer mentorship, social support mentorship) twice per month. Mentorship and social support supervision will occur separately. Between scheduled supervision, mentors may contact Drs. [name] or [name] to discuss emergent questions/concerns. In urgent situations, mentors may contact the EDRU psychiatrist on call. In emergencies, mentors will be told to call 911. Over any period that a leader (mentor or volunteer) is providing the intervention, he/she will be required to attend the bi-monthly supervision and if necessary make up missed sessions. Supervision will focus on both clinical issues that arise during meetings with participants as well as treatment fidelity and adherence to the content of the intervention.

Mentees and all mentors will be asked to submit the “weekly report” form (Appendix 1) each week, to determine number of contacts and session content. **Peer mentors** only will also be asked to fill out the post-treatment peer mentor rating form (Appendix 2). All fidelity monitoring forms will be reviewed by Drs. [name] and [name] on a weekly basis, and the information will be used to guide supervision sessions. This information will also be used to evaluate fidelity to intervention content (for both conditions).

Additional procedures to optimize participant safety:

(1) Distinguishing between supportive interventions versus treatment: The distinction between supportive interventions versus treatment (described on pages 64-65 of Communities of HEALing manual) will be underscored throughout screening and intervention procedures. We will identify mentorship and social support as *adjunct*, supportive interventions intended to supplement treatment. We will ensure, through documentation and monthly contact with providers, that patients are concurrently enrolled in treatment with a licensed provider. If a participant stops attending outpatient treatment, the study investigators will discontinue his/her participation in the active interventions (meetings with mentors). This is to ensure that all participants who are meeting with mentors also have outpatient teams. These concepts will be outlined during telephone and in-person screenings, when reviewing study consent, during first meeting between mentor/mentee and at subsequent meetings when deemed necessary, and at the beginning of community support groups.

(2) Ensuring participants are engaged in outpatient treatment with a licensed provider: All mentees provide documentation of ongoing engagement in treatment with licensed provider in order to start and continue meeting with a mentor. If a patient misses a doctor form, he/she and his/her mentor will be asked to discontinue meetings until the form is obtained. Once a form is submitted, participants and their mentors may resume meetings for the duration of the six month randomized period. If the research team does not receive any additional forms, participants may continue completing questionnaires if they wish. Because completing surveys via Qualtrics is only minimal risk, we will ask participants to continue completing surveys even if they discontinue mentorship meetings. A patient may decline to continue completing the questionnaires.

If a participant is on the wait list, they must submit a provider form for month 6 (the conclusion of the wait-list period) in order to be matched with a mentor. If a participant does not submit a provider form, he/she may not be matched with a mentor, but they may continue completing assessments if they wish.

(3) Training and procedures to address suspected risk to a mentee's health or safety: Participants will provide documentation of permission for their mentor or EDRU research staff to contact their treatment provider in the case of emergent clinical/medical issues. All peer mentors and social support mentors receive training in how to recognize and respond to concerns about a mentee, including potential clinical deterioration, medical instability, or psychiatric instability (e.g., suicidal thoughts or behavior). Specific to suicide risk, this training includes information about signs of suicidal thoughts/behaviors and how to respond to concern about suicidality. Since peers are *not clinicians*, they will be advised to do the following in any case of imminent risk: 1) Contact emergency services 2). Contact EDRU supervisors immediately (Drs. [name] and [name]). In cases when the mentor is not concerned about imminent risk: 1). Encourage the mentee to raise the issue with his or her treatment team; 2). Contact EDRU supervisors.

Assessments: All participants will complete monthly assessments of eating disorder symptoms, eating disorder quality of life, and co-morbid psychiatric symptoms throughout the six month randomized phase and then again at a 12-month follow up time point. Participants assigned to the wait-list condition will also complete monthly assessments throughout the "open label" phase in which they are receiving mentorship. On a monthly basis, patients' treatment providers will be contacted in order to obtain the patient's current height/weight from which to calculate BMI. Patient questionnaires will be administered using Qualtrics, a HIPAA-compliant applications accessible by smart phone or computer. If, during participation in an intervention or wait-list condition, a participant is hospitalized or returns to a higher level of care (e.g., residential treatment, partial hospitalization), he/she may resume participation in the mentorship component of the study only with permission from his/her treatment provider (a new letter must be obtained from primary provider). **All participants will complete a questionnaire assessing study acceptability of the study at the end of the 6 months period of mentorship or as soon as their participation in the study ends (e.g., if a participant discontinues after 3 months, they will be asked to complete the survey at that time).**

Mentor Procedures:

Individuals participating as mentors will be asked if they are willing to allow the study team to utilize data previously collected as part of interviewing and training to be a mentor. This data includes demographic information such as age and gender, as well as diagnostic history, for the peer mentors. Mentors will be informed about the study during a supervision call with the PI of the study and Project HEAL staff. Prior to reviewing the consent form during the telephone call with all mentors, all mentors will be sent a copy of the consent form to review ahead of time. Mentors will be asked to then speak individually with one of the study team members (the PI, a trained RA or other study clinician) to indicate whether or not they wish to participate in the study.

The information collected as part of the process of interviewing to be a mentor will be sent in a de-identified format. The code linking mentor information with the identifier will be transmitted by phone to the study team. Mentors will also be asked to fill out a brief 4-question survey using Qualtrics.

Blood and other Biological Samples

Describe how the sample will be used and indicate, when relevant, the amount of the sample. The IRB wants to know that the sample is sufficient for the purposes of the study, but that sampling is limited to what is minimally necessary.

If you've indicated that you intend to store a sample for future use, indicate where the sample will be stored, how long the sample will be stored, and to what purposes the sample will eventually be put. Check the IRB website at <http://irb.nyspi.org/irbdnn/Policies/GeneticResearch/tabcid/96/Default.aspx> for specific guidance and additional information about future use of DNA samples.

Neither blood nor other biological samples will be collected.

Assessment Instruments

List all assessment instruments, indicate who will administer them, and provide an estimate the duration of each. The IRB wants to know that assessments instruments are appropriate measures for the purposes of the study and are no

more burdensome than is necessary. The IRB will consider the burden of assessment instruments (in terms of time, sensitivity of material, etc.) in the risk/benefit analysis. Please attach copies or otherwise provide all non-standard instruments.

Demographic information: Participants will be asked to report general demographic information including birth date, sex, race/ethnicity, and socioeconomic status.

Height and weight: Participants will sign consent giving the research team Project HEAL Program Directors permission to contact their outpatient provider on a monthly basis to receive documentation of height/weight.

Eating Disorder Symptoms: Eating disorder symptoms will be assessed monthly using the Eating Pathology Symptoms Inventory (1). The Eating Pathology Symptoms Inventory (EPSI) is a self-report questionnaire that includes 45 items covering 8 subscales: Body Dissatisfaction, Binge Eating, Cognitive Restraint, Purging, Restricting, Excessive Exercise, Negative Attitudes toward Obesity, and Muscle Building. Each item is scored on a five-point Likert-style scale (0 = Never; 4= Often) to describe how well each item describes the participant's experiences. Scores are derived by summing responses across the questions included in each subscale. The EPSI is part of the Phynx Toolkit, a NHGRI/NIDA-sponsored catalog of recommended standard measures of phenotypes (symptoms) for use in biomedical research. To assess frequency of bingeing and purging episodes, BN and BED patients will be asked to report the average number of episodes/week experienced within the past month on each monthly report of symptoms.

Eating Disorders Quality of Life: Quality of life as related to the patient's eating disorder will be measured using the Eating Disorder Quality of Life assessment survey (2). The EDQOL is a 30-item measure assessing the impact of the eating disorder on psychological, physical/cognitive, financial and work/school domains of life. Participants indicate the extent to which the eating disorder has resulted in a variety of consequences within the past 30 days (e.g., "How often has your eating disorder led to low grades?" on a 5-point scale ranging from 1 = "never" to 5 = "always." Higher scores indicate higher levels of QOL impairment. The measure has been validated and demonstrates good psychometric properties.

Comorbid psychiatric symptoms: Anxiety symptoms will be measured using the State Trait Anxiety Inventory (STAI) (3).The STAI is a well-validated 20-item measure used to assess trait-level anxiety. Each item is rated on a scale of 0 – 2, with total scores ranging from 0 – 40. Depressive symptoms will be measured using the Patient Health Questionnaire-9 (PHQ-9), a 9-item self-report questionnaire commonly used in clinical practice. The PHQ has demonstrated good psychometric properties and has high sensitivity and specificity (4).

Health Care cost: Estimated total health care costs related to the patient's eating disorder will be assessed using the Health Care Cost and Utilization Survey, developed by the research team. The survey asks participants to report the types and frequencies of a range of health services received including hospitalizations, residential treatment, outpatient visits (e.g., primary care, registered dietician) and tests (e.g., urine test, blood test), and mental health treatment (e.g., individual therapy, family therapy). Patients are also asked to report information pertaining to their insurance coverage and amount/percentages paid out-of-pocket for various services.

Acceptability of the study: Acceptability of the mentorship programs will be assessed using the Study Acceptability Form developed by the research team, modified from existing evaluation measures. The questionnaire asks participants to report on their experience with mentorship on dimensions of helpfulness, appropriateness, overall experience, matching expectations, recommend to friend, as well as specific questions pertaining to the alliance with mentor. Participants rate their answers on a 5- or 7-point scale or in open-ended dialogue boxes.

Research Related Delay to Treatment

Research involving participants who are in need of treatment invariably involves delay to care, and this delay is associated with risk. Scheduling of procedures must be carefully organized to minimize delay. Other delay must involve only that minimally necessary to accomplish the aims of the research while respecting subject well-being and safety. Describe the delay, by virtue of research participation in this study, before a participant can receive treatment of known efficacy or standard care routinely offered in the community.

All participants will be enrolled in treatment with a licensed provider concurrent with their participation in either peer mentorship, social support, or wait-list. The study involves three intervention arms, two of which are active (peer mentorship, social support) and one of which is a wait-list control. For individuals assigned to mentorship or social support, there may be a delay to intervention if a mentor or volunteer is unavailable to meet with the participant at the time that he/she enrolls in the study. For participants assigned to the wait-list, there will be a six-month delay before the participant receives an active intervention.

Clinical Treatment Alternatives

Describe what other treatment or assessment options are available to subjects who do not participate in research.

All participants will be required to be engaged in a form of outpatient treatment with a licensed provider in order to be randomized to a condition, and in order to meet with their mentors. Alternatives to participation include not participating. Participants attending Communities of HEALing chapters who choose not to participate in research may still attend support groups offered by Project Heal but they will not have the option of being paired with a mentor.

Risks/Discomforts/Inconveniences

"Risk" is a broad term used to convey the potential for harm, burden, and inconvenience related to research participation. Use this section to provide a comprehensive description of foreseeable physical, psychological, social, interpersonal, and economic risks introduced by the research. Include the source of the information. Consider both the probability and magnitude of harm and its impact. Describe the foreseeable harms associated with the research (untoward effects of a medication) and those related to delay to individualized treatment. Include data from the literature, and local data, if available, on risk rates and subject experiences with research procedures. Describe procedures in place to minimize risk. In general, please create a numbered list of risks/categories of risk, and in general put the list in the order of significance or level of risk, the most significant risks first followed by others.

1. Psychological assessments Participants may feel distressed or bored as a result of completing study assessments.
2. Risk of clinical deterioration There is a risk that some participants might experience a deterioration of their psychiatric or physical condition over the course of the study.
3. Risk of unintentional disclosure of confidential information **This risk applies to both mentees and mentors.** There is a risk that sensitive information collected in the study could become known to individuals not involved in the study.

Procedures in place to minimize risk:

1. Psychological assessments If a research participant experiences distress as any part of the screening process, then an EDRU clinician will be available to talk with the participant. Participants will be informed that they should contact a EDRU clinician if they experience distress while filling out assessment questionnaires.
2. Clinical deterioration If a participant is suspected to be at risk for relapse or otherwise medically/psychiatrically unstable, mentors and/or EDRU research staff will contact the patients' treatment team and/or emergency services. Mentors in both active intervention conditions will receive training in how to respond to situations in which the participants' medical/psychiatric stability is questionable. Mentors and volunteers will receive ongoing (bi-monthly) supervision by a MD or PhD level EDRU clinician with expertise in the treatment of eating disorders. The risk of clinical deterioration is also minimized by ensuring (through monthly contact with outpatient provider) that all participants, including those on the wait-list, are concurrently enrolled in outpatient treatment, expected to minimize risk of clinical deterioration.

3. Risk of unintentional disclosure of confidential information All procedures are consistent with HIPAA requirements, including the completion of online assessments using Qualtrics. Research data will be de identified and stored in locked rooms and computer records will be identifiable only by a participant's deidentified study code. PHI will be available to individuals outside the clinic only if requested in writing and if the participant has signed a release form. Patients will

receive a notice of privacy policies and be asked to sign a HIPAA form in addition to the consent form. **Additionally, data regarding the mentors will be provided to the research team by Project Heal in de-identified form. The key to the codes will be given to the research team by phone in a confidential setting.**

Methods to Protect Confidentiality

Describe the data management plan and the methods you will employ to protect subject privacy and the confidentiality of research data. The section should detail how information will be collected, recorded, coded, stored, transmitted, and as applicable, shared with other investigators so as to minimize risks related to breach of confidentiality. Confirm that identifiers are removed, to the extent possible, from research data, and explain if there are links between subject identity and research data, or if the data is anonymous. Also, indicate where the data is stored, who is responsible for its safekeeping, and who has access to subject identity and codes, if any, which cross-link research data and subject identity. Confirm that identifiable data is not collected, stored, or transmitted by mail, fax, on removable drives, laptops, or via the internet without proper protections, e.g. encryption.

To protect patient confidentiality, all data collected will be kept confidential and used for professional purposes only. Information will be available to the patient's physician or other health services only if directly requested in writing and the participant signs a release form. Identifying information will be kept separate from research records. All patient records at NYSPI will be kept in secure, locked offices within the facilities, and all forms will be identified with only the study code. All electronic data will be stored on computers that are password protected. Only code numbers will appear on any data and documents used for evaluation or statistical analyses. Publications using this data will be done in a manner that fully protects subjects' anonymity.

Direct Benefits to Subjects

Describe only benefits to individual subjects that are likely to accrue during the study itself. Do not include subject compensation or treatment to be provided at the end of the study, as these do not figure into the IRB's risk benefit considerations. Do not describe diagnostic and evaluation components unless subjects receive clinical feedback. Do not describe the anticipated scientific benefits of the research. Some studies offer no direct benefit to subjects.

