To evaluate feasibility, we will monitor mentee attendance and acceptability in both active conditions. To evaluate fidelity, mentors and mentees will be asked to complete a brief form (Appendix 1, “weekly report”) assessing meeting logistics (e.g., where the meeting occurred, number of contacts per week outside of meeting) and content of the meeting (e.g., topics discussed, activities). Peer mentors will be asked to complete an additional questionnaire assessing adherence to the peer-mentorship manual (Appendix 2, post-meeting mentor rating). Participants’ eating disorder symptoms, comorbid psychiatric symptoms, and health care costs and utilization will be assessed at pre- mid- and post-treatment to evaluate preliminary efficacy. Participants’ weight and BMI trajectories will also be evaluated by obtaining weight measures from the participant’s outpatient provider with participant permission. Outcomes for individuals who participate in the peer mentorship program will be compared with individuals who participate in the social support and wait-list conditions. **We will also evaluate characteristics of individuals participating as peer and social support mentors, including whether demographic characteristics and diagnostic history influence outcome of the mentorship.**

Specific Aims and Hypotheses

Concisely state the objectives of the study and the hypothesis or primary research question(s) being examined. There should be one hypothesis for every major study procedure or intervention. For pilot studies, it is important not to overstate the study's objectives. If there are no study hypotheses, describe broad study goals/aims.

Primary Aims and Hypotheses:

Aim 1. Evaluate the feasibility and acceptability of peer mentorship. Hyp 1a. Peer mentorship will demonstrate greater feasibility, as measured by higher attendance rates, compared to the active control intervention. Hyp 1b. Peer mentorship will demonstrate greater acceptability, as measured by higher acceptability ratings, compared to both control conditions.

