Aim 2: Evaluate the impact of intervention condition on eating disorder symptoms. Hyp 2a. Participants in peer mentorship will have greater reductions in eating disorder symptoms, measured using the Eating Disorder Symptom Inventory (EPSI), compared to both control conditions. Hyp2b: For individuals who meet criteria for current or past anorexia nervosa, individuals assigned to peer mentorship will be more likely to achieve or maintain a BMI ≥ 18.5 , compared to both control conditions. Hyp2c: For individuals who meet criteria for current or past bulimia nervosa or binge eating disorder, individuals assigned to peer mentorship will be more likely to abstain from bingeing/purging and bingeing episodes, respectively, compared to individuals in either control condition.

Aim 3: Evaluate the impact of intervention condition on total cost for eating disorder treatment. Hyp 3. Estimated total cost for eating disorder treatment, measured using the Healthcare Utilization Survey, will be lower among peer mentorship participants compared to both control groups at (i) post-treatment and (ii) one-year follow up.

Exploratory Aim: Evaluate characteristics of individuals participating as peer and social support mentors. Exploratory hypothesis: Mentor characteristics and similarity between mentee and mentor characteristics will not influence mentee outcomes (acceptability, eating disorder symptoms, and estimated treatment cost).

Inclusion/Exclusion Criteria

This section details your study sample(s) and addresses the requirement for risk minimization. You may choose to divide your sample by population (healthy controls vs. subjects) or by procedure (subjects who will have an MRI) and then define different sets of criteria for each.

For each sample, create or insert a table to describe detailed criteria for study inclusion and exclusion and the method you will use to ascertain each criterion. The method of ascertainment may describe tests, scales and instruments. When relevant, indicate the level of training of the person who will make the assessment (e.g. clinical interview by a psychiatrist).

Inclusion/Exclusion Criteria needs to be numbered and listed in outline form (see Table template below)

Mentees (Adolescents or adults with anorexia nervosa, bulimia nervosa, or binge eating disorder):

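### Hyp 1b's wait-list comparison does not fit the acceptability form as described, and the SAP's longitudinal model does not suit one rating per person

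*Protocol*

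**What the plan says.** - **Hypothesis.** Protocol, Specific Aims and Hypotheses, Hyp 1b: "Peer mentorship will demonstrate greater acceptability, as measured by higher acceptability ratings, compared to both control conditions". The controls are social support and the wait list. Hyp 1a, just before it, compares attendance with the active control only.
- **Instrument.** Protocol, Assessment Instruments, Acceptability of the study: the form asks "participants to report on their experience with mentorship on dimensions of helpfulness, appropriateness, overall experience" and further dimensions, "as well as specific questions pertaining to the alliance with mentor". Items use 5- or 7-point scales or open text.
- **Exposure.** Protocol, Research Related Delay to Treatment: "For participants assigned to the wait-list, there will be a six-month delay before the participant receives an active intervention". Background, Significance, and Rationale adds that wait-list participants are then offered a mentor for six months and may choose either type. Under Additional procedures to optimize participant safety, those without a month-6 provider form may not be matched at all.
- **Timing.** Protocol, Study Procedures, Assessments: "All participants will complete a questionnaire assessing study acceptability of the study at the end of the 6 months period of mentorship". Anyone who leaves before then is asked for the form on leaving. No separate time point is given for the wait list.
- **Monitoring.** Background says that, to evaluate feasibility, "we will monitor mentee attendance and acceptability in both active conditions".
- **Analysis.** The SAP uses linear mixed models for each outcome, with time, three-level group and their interaction as predictors and a random intercept in all models. Peer mentorship is the reference group and is compared with each control.
- **Exploratory aim.** Acceptability is also one of the mentee outcomes to be related to mentor characteristics.

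**The concern.** Two separate things do not fit together.

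First, the hypothesis asks the wait list for ratings of something it has not received in the randomised period. If wait-list participants complete the form before being matched, the items on mentorship and on the mentor have no referent. If they complete it after their later mentorship, they rate an intervention given after the randomised comparison has ended, which may be the very intervention it is meant to be compared with. Because early leavers are also asked, both kinds of rating could occur within one arm.

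Second, the only analysis model in the SAP is built for repeated measurements, while the form is completed once. An analyst following the SAP could not fit the stated model to acceptability, and would have to choose another one unplanned, for a hypothesis listed under the primary aims. The exploratory aim has the same gap.

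**Working it through.** The documents give no alpha, power, effect size or standard deviation for acceptability, so there is no stated figure to reproduce. The check is whether the stated comparison and model can be carried out.

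**1. What the wait list can rate, by time of completion**

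| When the form is completed | Study mentor so far | Consequence |
|---|---|---|
| Month 6 | none | mentorship and alliance items have no referent |
| Exit before month 6 | none | same |
| Exit, never matched | none | same |
| About month 12, after mentorship | self-chosen peer or social support mentor | rating lies outside the randomised comparison |

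**2. Illustration for ratings at about month 12**

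Assume that ratings depend only on mentor type. Let m be the mean with a social support mentor, D the peer-minus-social difference, and p the share of the wait list with a peer mentor. Neither p nor D is in the documents.

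- Peer arm mean: m + D.
- Wait-list mean: p(m + D) + (1 − p)m = m + pD.
- Contrast: D − pD = D(1 − p), which is D, 0.75D, 0.5D and 0 at p = 0, 0.25, 0.5 and 1.

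**3. Fixed effects with one row per person**

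Taking time as linear (the SAP does not say), the columns are the intercept, two arm indicators, time and two arm-by-time terms: 6 in all. This is equivalent to a separate intercept and slope in each arm. An arm therefore contributes 1 to the rank if all its members rate at the same time, and 2 if there are at least two distinct rating times.

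| Rating times | Peer + social + wait list | Rank of 6 |
|---|---|---|
| All at month 6 | 1 + 1 + 1 | 3 |
| Active arms month 6, wait list month 12 | 1 + 1 + 1 | 3 |
| Month 6, with one month-3 leaver in one arm | 2 in that arm, 1 in each other arm | 4 |
| Active arms month 6, wait list split between months 6 and 12 | 1 + 1 + 2 | 4 |
| An early leaver in each active arm, wait list split between months 6 and 12 | 2 + 2 + 2 | 6 |
| An early leaver in every arm | 2 + 2 + 2 | 6 |

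Full rank needs two distinct rating times in every arm, whatever their cause. Even then the slopes compare different people who rated at different times.

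**4. Variance components**

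With one record per person, Var(Y) = random-intercept variance + residual variance. Only the sum enters the likelihood, so the information rank is 1 of 2. In one simulated set of 80 ratings with total variance 1, the log-likelihood was −104.4246 for splits of 0, 0.25, 0.5, 0.75 and 1. With monthly data over months 0 to 6, the fixed effects have rank 6 of 6 and the variances 2 of 2, so the model is suited to the repeated outcomes.

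**5. The model that does fit**

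Peer versus social support with arm as the only predictor has 2 columns and rank 2. For scale, assume 1:1:1 allocation, two-sided alpha 0.05, 80% power and no mentor clustering (none of these is stated). The detectable difference is (1.960 + 0.842) × √(2/n) standard deviations:
- 80 completers, n = 80/3 = 26.7 per arm: 0.77 SD.
- 100 enrolled, n = 100/3 = 33.3 per arm: 0.69 SD.

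**The case against.** The strongest reply is that the form may be about the study as well as the mentor. It is called the Study Acceptability Form, the Assessments text speaks of acceptability of the study, and the amendment rationale says it was added partly to learn about mentees' experience of the study. A wait-list participant could perhaps answer items on overall experience or on recommending to a friend. This stands in part. A reader might infer that the wait list can rate nothing at all, but the documents do not support that, because the form is not among them. Satisfaction with waiting would still be a different construct from acceptability of mentorship.

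Other stronger readings also go too far:
- **That wait-list timing is missing.** A rule for all participants exists. Read literally, it puts matched wait-list participants at about month 12 and others at exit. It is ambiguous, not absent.
- **That the Background sentence on both active conditions contradicts Hyp 1b.** It concerns feasibility monitoring and does not say that acceptability is collected only there. The two are in tension.
- **That the time terms can be estimated only if people leave early in every arm.** The table shows that split wait-list timing can also contribute.
- **That D(1 − p) bounds the contrast.** Choice of mentor or the six-month wait may itself shift ratings, and the contrast could then fall outside 0 to D.

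A statistician could also simply drop the time terms and the random intercept at analysis. That would work for peer versus social support, but it should be planned. The SAP is dated 3/23/2018 and the uploaded protocol summary is labelled 5.18.18, so the SAP may not have been updated for the added form. That would explain the gap without closing it.

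**Conclusion.** The point holds, and should be fixed. On the form as described, Hyp 1b's peer versus wait-list comparison either lacks mentorship ratings in the wait-list arm or uses ratings made outside the randomised period. Confidence in that mismatch is moderate, because the form cannot be seen. The model finding is firm and rests on one rating per person, as the Assessments text describes. The random-intercept and residual variances are never separable. With linear time, the fixed effects have rank 3 of 6 when each arm rates at one time; if rating times vary enough for full rank, the time terms still do not measure change within a person.

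The effect is confined to acceptability, in Hyp 1b and in the exploratory aim. A reader might infer that Hyp 1b as a whole is untestable, but peer versus social support remains interpretable with a suitable model. Nothing here touches the symptom or cost hypotheses.

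**What to change.** - **Hyp 1b.** Restrict the confirmatory test to peer mentorship versus social support, using the one form completed at month 6 or at discontinuation.
- **SAP.** Add a short paragraph for acceptability: one rating per participant, arm as predictor, no time terms and no participant random intercept, analysed as randomised. Name the score, since items are on different scales, and report form completion by arm. Allow for clustering where one mentor has several mentees, as the social support condition permits. Say which mentor a rematched participant rates.
- **Exploratory aim.** Use the same one-rating approach for acceptability, with the mentor characteristic as predictor and mentor clustering allowed for.
- **Wait list.** State in Study Procedures, Assessments, when this arm completes the form. Report its ratings of later mentorship descriptively by mentor type, outside the randomised comparison.
- **Separate inconsistency.** The lay summary in the application form says that the wait list later receives peer mentorship. The protocol summary's lay summary says either type, and its Background says participants may choose. These must be reconciled.

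The cost is a rewording of Hyp 1b, a sentence on timing and a SAP paragraph, with no new data. The protocol summary copy with draft date April 10, 2018 needs the same Hyp 1b and timing edits only if it is still in force. The downside is that the peer versus wait-list acceptability claim is given up.
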